1. Evidence of a personally signed and dated informed consent document (and assent document, as applicable) indicating that the subject (and/or a legal representative/guardian(s) as applicable according to subject age and local guidelines) has been informed of all aspects of the withdrawal/re-treatment period of the study. Only one informed consent document/assent will be signed and dated for the withdrawal/re-treatment period.
2. The subject is willing and able to comply with all applicable aspects of the withdrawal/re-treatment period of the study, including scheduled visits, treatment plan, laboratory tests, and other study procedures.
3. The subject and/or the parent or legal representative/guardian of the subject must be able to provide contact information, including primary care physician or other treating physician.
4. For subjects entering directly into the withdrawal/re-treatment period, have completed approximately 96 weeks of investigational product in study 0881A1-3338.
5. For subjects entering directly into the withdrawal/re-treatment period, the baseline visit in study B1801023 must be completed within 14 days of the last dose of investigational product in study 0881A1-3338.
6. The subject has met the Wallace definition for clinically inactive disease for at least 6 months on investigational product (etanercept) or, in the investigator's judgment,

has had a good clinical response and would benefit from withdrawal from investigational product.

7. The subject, parent, or legal representative/guardian of the subject must be able to read and complete the protocol-specified efficacy assessments.

4.1.3.1. Additional Inclusion Criteria for Subjects Planning to Restart Investigational Product in the Re-treatment Period

1. Re-treatment with investigational product should be based on the investigator's clinical judgment as long as all other inclusion/exclusion criteria for re-treatment period are met.
2. Either the subject or an available adult must be capable (according to the investigator's judgment) of reconstituting and administering injections of subcutaneous (SC) etanercept.

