2.2. Study Design

2.2.1. Basic Features of the Study Design

This is an open-label, single treatment, multi-center, 8-year extension study in pediatric subjects who have been diagnosed with one of 3 subtypes of JIA (eoJIA, ERA, or PsA), have received at least one dose of etanercept and completed approximately 96 weeks of participation in study 0881A1-3338-WW (B1801014). These subjects will be asked to participate in study B1801023. It is anticipated that approximately 100 subjects will be enrolled in study B1801023. This 96-month study contains 3 periods: an active treatment period, a withdrawal/re-treatment period, and an observational period.

Active treatment period

Subjects who completed approximately 96 weeks of active treatment with investigational product (etanercept) in study 0881A1-3338-WW (B1801014) and are eligible to continue investigational product in study B1801023 will enter directly into the active treatment period. These subjects may continue to receive investigational product for up to 8 additional years (96 months).

Withdrawal/Re-treatment period

Withdrawal: Subjects who have either completed approximately 96 weeks of treatment in study 0881A-3338 or were enrolled in the active treatment period of study B1801023 and who have either met the Wallace definition for clinically inactive disease for at least 6 months on investigational product (etanercept) or who, in the investigators judgment, have had a good clinical response and would benefit from withdrawal from investigational product and are otherwise eligible can enter the withdrawal/re-treatment period. However, the withdrawal/re-treatment period is optional and it is ultimately up to the investigator and subject to determine when the subject should be withdrawn from treatment.

Re-treatment: Subjects requiring re-treatment per the investigator's clinical judgment and who are otherwise eligible will be offered the option to re-start treatment with investigational product.

Subjects may not enter the withdrawal/re-treatment period more than once during the study.

Observational period

All subjects will be followed for a total of 8 years from the time of initial entry into the study as follows:

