3.2. Withdrawal Analysis Set

The withdrawal analysis set (WAS) will include those subjects who entered the withdrawal period. Only data collected in the withdrawal period will be included.

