5. ANALYSIS METHODS

All analyses will be performed for the overall population as well as each of the 3 JIA subtypes.

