5.9. Efficacy Endpoints

Descriptive summary statistics will be provided for efficacy endpoints. For continuous endpoints, the summary statistics at each visit will include the number of observations, mean, standard deviation, median, minimum, maximum and 95% confidence interval for the mean. These statistics will be provided for the observed value and change from baseline. The mean percent change from baseline will be provided also. For categorical endpoints, the summary statistics will contain the frequency, percentage, and 95% confidence interval (CI) for the percentage.

These summaries will be performed for:

- FAS, active period data (both parent and extension studies. Baseline of parent study will be used for calculation of change from baseline). The reports will show the baseline (no baseline for ACRPedi responses), weeks 12, 24, 48, and 96 from the parent study and all visits from the extension study where data is collected.
- WAS. The reports will show all visits where data is collected.

- RTAS. Re-treatment period baseline will be used for calculation of change from baseline. The reports will show all visits where data is collected.

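### In the withdrawal set, the pooled percentage with inactive disease cannot be read as inactive disease kept: entry status is mixed, and subjects who relapse leave the denominator

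*SAP*

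**What the plan says.** Protocol 4.1.3, item 6, gives two alternative routes into withdrawal. One is Wallace clinically inactive disease for at least 6 months on etanercept. The other is that the subject, in the investigator's judgement, "has had a good clinical response and would benefit from withdrawal from investigational" product. The second route sets no score and no duration. Protocol section 3 and SAP 2.2.1 repeat the two routes.

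SAP 3.2 then defines one set: "The withdrawal analysis set (WAS) will include those subjects who entered the withdrawal period". It adds: "Only data collected in the withdrawal period will be included".

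Clinically inactive disease is a listed efficacy endpoint (SAP 4.2.2). Under SAP 5.9 it receives a frequency, a percentage and a 95% confidence interval. The instruction for this set is "WAS. The reports will show all visits where data is collected". SAP 5.9 names a baseline for change in the full analysis set and the re-treatment set, but none for WAS.

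The only stated breakdown is in SAP 5: "All analyses will be performed for the overall population as well as each of the 3 JIA subtypes". SAP 5.4 summarises WAS at the withdrawal baseline, but its listed items include neither inactive-disease status nor entry route. SAP 5.16 does not impute an endpoint that is still missing after derivation.

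**The concern.** SAP section 1 gives the amendment's purpose as exploring benefit and function once etanercept is withdrawn. Protocol 1.2 gives the background: little is known about when or how to stop after a good response. Much of the evidence it cites starts from patients who were inactive when treatment stopped. A reader will want to set the WAS result beside those figures and will ask how many who stopped with inactive disease kept it.

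The planned percentage does not answer that, for two reasons:

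- **Mixed starting status.** A subject who was not inactive on stopping, and is not inactive later, counts against the percentage although no inactive disease was lost.
- **Departing subjects.** A subject who relapses moves to re-treatment or observation (Protocol 6.1.5 and the withdrawal schedule footnotes). That subject then contributes nothing to later WAS visits, so the remaining denominator is enriched for those doing well.

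The two effects work in opposite directions, and the planned tables allow neither to be removed.

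**Working it through.** The documents give no expected percentage, no number entering withdrawal and no split by route, so there is no planned figure to reproduce. What follows is illustration.

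**Inputs**

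- *r*, the share of subjects inactive at the withdrawal baseline who are still inactive at a visit: assumed 50%. Protocol 1.2 reports a 50% probability of staying symptom-free at 6 months in a retrospective review of 26 patients, all inactive when etanercept was stopped. That is not identical to Wallace status, so it serves only as a reference value.
- *p*, the share of WAS inactive at the withdrawal baseline: not in the documents; varied from 0.5 to 0.7.
- *g*, the share of the other entrants who are inactive at the visit: not in the documents; varied from 0 to 0.1.

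**Step 1: everyone stays.** Pooled = p·r + (1 − p)·g.

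- p = 0.5, g = 0: 0.5 × 0.5 + 0.5 × 0 = 25%.
- p = 0.7, g = 0.1: 0.7 × 0.5 + 0.3 × 0.1 = 38%.

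**Step 2: all who lose inactive disease leave WAS, and the others stay.** Pooled = [p·r + (1 − p)·g] / [p·r + (1 − p)]. Per 100 entrants:

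- p = 0.5, g = 0: 25 / (25 + 50) = 33%.
- p = 0.7, g = 0.1: (35 + 3) / (35 + 30) = 38 / 65 = 58%.

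The same 50% retention therefore appears as anything from about 25% to 58%, on both sides of the true value.

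**Step 3: a split alone is not enough.** Take only subjects inactive at baseline, with all who lose it leaving. For p = 0.7 the observed-case figure is 35 / 35 = 100%, against true retention of 35 / 70 = 50%. Fixing the denominator at the 70 who started inactive returns 50% whatever *p* is.

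**Step 4: adding only the pooled baseline percentage is not enough.** Suppose a share *b* is inactive at baseline and a share *f* at a visit, in the same subjects with no exits. Retention is then bounded by max(0, b + f − 1)/b and min(b, f)/b.

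- b = 0.6, f = 0.5: 0.1/0.6 = 17% to 0.5/0.6 = 83%.
- b = 0.8, f = 0.5: 0.3/0.8 = 38% to 0.5/0.8 = 63%.
- b = 1, f = 0.5: exactly 50%.

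Only a within-subject summary identifies retention, unless everyone enters inactive and nobody leaves.

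**The case against.** The strongest reply is that the plan asks a broader question. It sets out to describe what happens after stopping in subjects with inactive disease or a judged good response, and WAS is exactly that population. The SAP is descriptive and nowhere labels the percentage as remission kept. This stands: what is missing is a summary, and the existing one is not a false statement. The pooled figure should stay.

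Second, SAP 5.4 already describes WAS at the withdrawal baseline by physician global, joint counts, morning stiffness and CRP, which are most of the elements of inactive disease. This stands in part. Separate summaries of the elements do not show how many subjects met all of them together.

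Third, objectives, endpoints and the end of the SAP are partly redacted, and the readable text around Protocol 9.2.2 is broken. A split could sit there, so the point is limited to the readable text.

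Fourth, efficacy is secondary, about 100 subjects are expected and withdrawal is optional, so further division gives small cells. That is a real cost and limits the weight of the point.

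A reader might go further and infer that pooling understates retention, by 12 to 25 percentage points on the Step 1 figures (50 − 38 and 50 − 25). The documents do not support this. Step 1 keeps every subject in the denominator, whereas under SAP 3.2 and 5.16 subjects who leave drop out unimputed. With the same inputs the figure can then exceed 50%.

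**Conclusion.** The point holds as a gap in the readable plan: WAS combines subjects with and without inactive disease at entry, reports them on observed cases, and offers no summary from which retention can be recovered. The direction and size of the discrepancy are unknown. The range of about 25% to 58% against 50% rests on assumed values of retention, entry mix and later gain, and on the two extremes of no exits and complete exit of those who lose inactive disease. If nearly all subjects enter inactive, the mixing effect is small but the exit effect remains and pushes the figure upward.

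The primary malignancy endpoint is unaffected. This is a worthwhile, inexpensive improvement to a secondary descriptive result.

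**What to change.** - **SAP 5.4:** add clinically inactive disease status at the withdrawal baseline to the WAS table. Add entry route only if it is recorded; the schedules do not list it as a data item. Status is the essential split, since a subject admitted on judgement may also be inactive on stopping.
- **SAP 5.9:** keep the pooled WAS summary and add efficacy by that status.
  - *Inactive at the withdrawal baseline:* report retention with the denominator fixed at all such subjects, counting those who leave for relapse or re-treatment as not retained. State how other exits are handled. Time to loss of inactive disease is an alternative.
  - *Not inactive at the withdrawal baseline:* report change in JADAS and joint counts from that baseline.
  - Name the withdrawal baseline as the reference for change in WAS.

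**Cost:** SAP wording and programming. Joint assessment, physician global, CRP and morning stiffness are already scheduled at the active-treatment early withdrawal visit and at the direct-entry baseline (recent week 96 values may be used there). The remaining Wallace elements can be handled as at later visits. Intervals will be wide: with half retained, the exact 95% interval is about 19% to 81% for 10 subjects, 27% to 73% for 20 and 31% to 69% for 30. These group sizes are assumptions. Any relevant redacted text should be checked first.

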- h. The final observational visit will occur by telephone contact 96 months (± 4 weeks) after the baseline visit of study B1801023.
- i. For subjects in the withdrawal period, the following concomitant medications will be collected: DMARDs, corticosteroids, NSAIDs, and anti-infective agents. Only non-drug treatments received due to an adverse event will be collected.
- j. For subjects in the observational period, the following concomitant medications will be collected: DMARDs, including any immunosuppressives or anti-TNFs and/or other immunosuppressive biologic agents; corticosteroids; and anti-infective agents taken for medically important infections. Only non-drug treatments received due to an adverse event will be collected.
- k. Weight will be measured at every visit for subjects who are < 18 years of age and who weigh ≤ 62 kg. For those subjects who are ≥ 18 years of age or weigh > 62 kg, weight will be measured annually as part of the physical examination.
- l. Tanner Stage Assessment will be performed annually for subjects < 18 years of age or who have a score of < 5 on 1 or more applicable domain(s). The Tanner Stage Assessment does not need to be repeated at the re-treatment assessment visit if it was performed within 2 months before the visit.
- m. Additional laboratory testing may be performed according to local guidelines or standard of care and for follow-up of abnormal laboratory test results.
- n. The evaluation of childbearing potential in female subjects must be documented in the subject's source documents.
- o. Urine pregnancy tests will be performed at each of the visits in the withdrawal period for all female subjects who, in the opinion of the investigator, are of childbearing potential; this includes subjects who are menstruating at the time of the visit. For subjects entering directly into the withdrawal/re-treatment period, the baseline pregnancy test must be performed within 7 days before the baseline visit. Pregnancy tests will also be done whenever a menstrual cycle is missed during the withdrawal/re-treatment period or when potential pregnancy is otherwise suspected. Pregnancy tests may also be repeated as per request of IRB/IECs or if required by local regulations.

- p. Discussion of sexual activity and use of contraception must be documented in the subject's source documents.

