There are some limited data from retrospective studies in the literature regarding discontinuation of etanercept during disease remission. These data provide some support for the concept that etanercept can be withdrawn during remission, and in the event of relapse, restarted with a good clinical response. Remesal et al analyzed the progress of patients with JIA after discontinuation of etanercept and the clinical response to re-introduction of the drug in those who relapsed.⁵ This retrospective chart review of patients between 2004 to 2009 revealed that therapy with etanercept had been discontinued in 26 patients with JIA who had achieved inactive disease using the original definition from Wallace et al for clinically inactive disease.⁶ They note that the majority of patients (69%) relapsed after discontinuation of etanercept, the probability of remaining symptom-free at 6 months was 50%, and the response to re-introduction of treatment was satisfactory. They concluded that etanercept can be discontinued after an “as-yet undetermined period of disease inactivity,” given that even if there is a relapse of disease patients will respond to re-introduction of etanercept. Prince et al found similar results in 9 patients with JIA who experienced relapse after withdrawal of etanercept.⁷ Unlike Remesal et al, they found the period of remission after discontinuation of etanercept was not associated with the duration of inactive disease before the withdrawal of treatment nor the method of withdrawal used (i.e., tapering of treatment versus abrupt cessation), and all 8 patients re-treated with etanercept achieved subsequent remission of disease activity “promptly”. Finally, a retrospective chart review of 171 JIA patients receiving anti-TNF agents, between 1998 and 2009 has recently been reported by Baszis et al.⁸ Of the 171 patients included in the review, 75% received etanercept. Similar to the findings of Prince et al, no correlation between the risk of flare and the length of anti-TNF therapy after inactive disease was achieved was observed in this study. The median time to withdrawal of anti-TNF therapy after inactive disease was achieved was 6.1 months. Of the 136 patients with inactive disease at the time of cessation of TNF treatment, 25% experienced a disease flare within 3 months of the withdrawal of

CCI

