6.1.5. Re-Treatment Assessment Visit for Subjects in the Withdrawal Period

Subjects in the withdrawal period who experience disease relapse will be seen for a re-treatment assessment visit at the study site, which should occur as soon as possible after disease relapse. Subjects requiring re-treatment per the investigator's clinical judgment and who are otherwise eligible will be offered the option to re-start treatment with investigational product.

Subjects who are in the withdrawal period and discontinue (eg, for adverse events) or are ineligible for re-treatment with investigational product for any reason will be seen for a re-treatment assessment visit at the study site and asked to participate in the observational period. Once the subject is in the observational period, he or she can not resume investigational product for the remaining time in the study.

The following safety and efficacy evaluations will be performed at the re-treatment assessment visit:

1. Collect/update contact information, including primary care physician or other treating physician.
2. Concomitant medications (DMARDs, corticosteroids, NSAIDs, and anti-infective agents) and non-drug treatments received due to an adverse event.
3. Physical examination (performed by a physician).
 - The physical examination will include completion of the Tanner Assessment for subjects <18 years or who have a score of <5 on 1 or more applicable domain(s). The Tanner Assessment does not need to be repeated if it was performed within 2 months before the re-treatment assessment visit.
4. Vital signs: Temperature, blood pressure (mmHg) and pulse rate (beats/min, after sitting for at least 5 minutes).
5. Height (cm).
6. Weight (kg):
7. Laboratory evaluations (ie, hematology, blood chemistry, and CRP).
 - For subjects entering the re-treatment period, all laboratory evaluations must be completed before administration of the first dose of the investigational product. Results of the re-treatment assessment visit laboratory tests are not required for investigational product administration, but must be reviewed as soon as possible after the re-treatment assessment visit and before the first visit in the re-treatment period. If the re-treatment assessment visit laboratory results are consistent with the laboratory abnormalities described in the exclusion criteria in [Section 4.2.3.1](#) or the results are determined to be clinically significant by the investigator, the

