3.3. Re-treatment Analysis Set

The re-treatment analysis set (RTAS) will include those subjects who entered the re-treatment period. Only data collected in the re-treatment period will be included.

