4.2.2. Secondary Endpoints

The secondary endpoints include

- *the occurrence of serious adverse events (SAE, infectious and non-infectious events will be summarized separately),*
- *the occurrence of medically important infections (ie, an infection requiring hospitalization and /or parenteral [intravenous (IV), intra-muscular (IM)] anti-infective agents).*
- Hospitalization: For any hospitalizations, the admission date, discharge date and reason for hospitalization will be collected during the study.
- Death: For any deaths, date of death and cause of death will be collected during the study.

- Nonstudy medication: nonstudy medications are coded using the WHO Drug Dictionary (2006 Q3). The Prior, Concomitant, After (PCA) flag for nonstudy medications will be derived for both parent study and extension study (only for active treatment period):
 - Prior nonstudy medications are defined as any nonstudy medications taken before the first dose of investigational product taken at the start of the study,
 - Concomitant nonstudy medications are defined as any nonstudy medications taken during the treatment period (from the first dose to the last dose of the investigational product).
 - After nonstudy medications refer to any nonstudy medications taken after the last dose of the investigational product.(not applicable for observational period)
- Exposure: the total number of doses taken and exposure time.

The above endpoints will be collected for all subjects. The following endpoints will be collected only for subjects in the active treatment period, or withdrawal/re-treatment period in the extension study:

Non-serious adverse Events (Adverse events that occur up to 30 days after the last dose of investigational product will be counted as having occurred during the treatment period) This is applied for active and retreatment periods. If an AE started in active or retreatment period and continued into withdrawal or observational period, it will be only counted in active or retreatment period, it will not be counted in withdrawal or observational period again. If an event started in withdrawal or observational period, and after 30 days of the last dose of investigational product of active period or re-treatment period, this event will not be counted.

Occurrence of withdrawals from investigational product due to adverse events;

Laboratory evaluations (ie, hematology, blood chemistry, and CRP)

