5.16. Data Derivation and Missing Data Handling

The following rules will be used to derive the endpoints and handle the missing components. If an endpoint is missing after derivation, the missing value will not be imputed.

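### The withdrawal-period table of clinically inactive disease describes the subjects still observed, whatever rescue they have had, and should not be read as the share inactive off etanercept without rescue

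*SAP*

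**What the plan says.** - **Analysis.** SAP 5.9 gives the frequency, percentage and 95% CI for categorical efficacy endpoints. For the withdrawal analysis set (WAS) it adds only: "WAS. The reports will show all visits where data is collected".
- **Data used.** SAP 3.2 defines the WAS as everyone who entered the withdrawal period, using data from that period alone. SAP 3.3 does the same for the re-treatment set: "Only data collected in the re-treatment period will be included". SAP 5.16 states: "If an endpoint is missing after derivation, the missing value will not be imputed".
- **Endpoint.** Clinically inactive disease (SAP 4.2.2) has six items: active joints, systemic features, uveitis, CRP, physician's global assessment and morning stiffness. None concerns medication.
- **Relapse.** Protocol 6.1.5: "Subjects in the withdrawal period who experience disease relapse will be seen for a re-treatment assessment visit at the study site". The subject then goes to re-treatment or is asked to enter the observational period.
- **Permitted medication.** In the withdrawal period, Protocol 5.3.1 lets a subject start or switch a permitted DMARD (adults may add a second) and adjust daily oral steroid up to 10 mg. It also allows up to 3 oral bursts or IV/IM steroid doses and up to 6 joint or soft-tissue injections per calendar year. No visible rule ends the period because of these. TNF inhibitors other than study drug are prohibited.
- **Medication reporting.** SAP 5.12 counts nonstudy medication in the WAS by type. The prior/concomitant/after flag "will be derived for both parent study and extension study (only for active treatment period").

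**The concern.** SAP 1 says the protocol was amended to explore clinical benefit and physical function after etanercept is withdrawn and after relapse. Protocol 1.2 says little is known about when or how to stop. A clinician will therefore want to know how many children who stop are later inactive without etanercept, and how many of those needed something else.

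The WAS percentage can differ from that in two ways. Subjects who relapse contribute nothing after the re-treatment assessment visit, so later percentages rest on a selected remainder. And DMARDs, steroids and joint injections act on the scored items (joints, CRP, physician's global, stiffness), so a subject made inactive by new treatment is indistinguishable from one who stayed inactive unaided. Read as control off etanercept without rescue, the figure would be too high whenever either has happened.

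**Working it through.** The plan states no sample size, target or expected rate for the withdrawal period, so there is no figure to reproduce. The check has two parts.

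**1. What the table counts.** Take three subjects who enter withdrawal.

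- A stays inactive with nothing added: inactive at each visit.
- B flares, starts methotrexate and has a joint injection, and meets all six items at the next visit: also inactive, because the definition does not look at medication.
- C relapses and restarts etanercept: C remains a WAS member, but later data belong to the re-treatment set and no value is imputed, so C is in neither numerator nor denominator from then on.

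The denominator is not stated outright. That it means subjects with data at the visit is inferred from SAP 3.2 and 5.16.

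**2. Illustrative size.** Let p be the share inactive among those remaining, r the share of entrants who have left on relapse, and s the share of remaining inactive subjects with new rescue for JIA.

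- Planned percentage = p
- Inactive off etanercept, of all entrants = p × (1 − r)
- The same, without new rescue = p × (1 − r) × (1 − s)

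Inputs: p = 80% and s = 0 to 30% are assumptions. For r, Protocol 1.2 cites one retrospective series in which "25% experienced a disease flare within 3 months" of stopping, and another in which "the probability of remaining symptom-free at 6 months was 50" per cent. That these shares would leave the withdrawal period here is an assumption.

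| Case | r | Planned | All entrants, s = 0 | s = 10% | s = 30% |
|---|---|---|---|---|---|
| No relapse | 0 | 80% | 80% | 72% | 56% |
| Month 3 | 25% | 80% | 60% | 54% | 42% |
| Month 6 | 50% | 80% | 40% | 36% | 28% |

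For example, 0.80 × (1 − 0.50) × (1 − 0.30) = 28%. With an assumed 40 entrants and half gone, 20 remain and 16 are inactive: 16/20 = 80% (Clopper-Pearson 95% CI 56.3 to 94.3) against 16/40 = 40% (24.9 to 56.7).

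**Sensitivity.**

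- *Symptom-free series.* Applying p = 80% to subjects already called symptom-free takes off a further fifth. With p = 100%, the Month 6 comparison is 100% planned against 1.00 × (1 − 0.50) = 50% of entrants.
- *Relapse visit counted.* The re-treatment assessment visit is a column of the withdrawal schedule and has full efficacy assessments, so a relapse may be counted once. Visit windows are left to a separate programming document (SAP 5.1). With 40 entrants, 10 relapsed by Month 3 and 24 of the other 30 inactive: if all 10 relapse visits fell in the Month 3 window, the planned figure would be 24/40 = 60%, with no gap. At Month 6, if only the next 10 relapses were windowed there, it would be 16/30 = 53% against 16/40 = 40%. The gap returns because the first 10 have dropped out.
- *Wider grid.* With 20 or 40 entrants, 25, 50 or 69% gone, 80 or 90% of the remainder inactive and 0 to 40% rescued, all rounded to whole subjects, the observed-case figure runs from 80 to 93% and the share of all entrants inactive without rescue from 15 to 70%.

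**The case against.** **Redaction.** The strongest objection is that a relapse or rescue analysis may sit in withheld text. Redactions follow the objectives in both documents, the endpoint lists and SAP 5.16.5, and the visible text of Protocol 9.2.2 breaks off before its end. This stands. A reader might infer that the plan has no relapse analysis, and the documents do not support that. A withheld analysis would not, however, change how the visible 5.9 table scores inactive disease.

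**No such claim is made.** No visible text says that the WAS table shows control without rescue. SAP 1 speaks of benefit after withdrawal, not of benefit without DMARDs. This also stands: the table is valid for what it describes, and the risk lies in how it is read.

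**Relapsers are not removed from the WAS.** A reader might infer that they are. SAP 3.2 includes everyone who entered the period. Only later data are excluded, and the relapse itself may appear once.

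**Other tables help.** Falling numbers by visit show departures. For subjects who began in the active period, SAP 5.3 gives the numbers entering withdrawal/re-treatment, the numbers switching to observation and the reasons for switching. SAP 5.4 baseline tables show how many entered the WAS and the re-treatment set. This narrows the point, but none of these tables links departure or medication to inactive status at a visit, and the by-type count in SAP 5.12 does not separate new drugs from continued ones.

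**A strict composite would overcorrect.** Entry does not require inactive disease, since an investigator-judged good response suffices (Protocol 4.1.3). Treating one joint injection as failure for the rest of follow-up would be harsh. Both points are accepted and shape the remedy.

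**Conclusion.** The point holds in a limited form. On the visible text, the by-visit WAS percentage is an observed-case figure with no medication condition. It describes those still in the withdrawal period and should not be quoted as the share of children inactive off etanercept without rescue.

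The size cannot be fixed from the documents, which give no rescue rate and no number entering withdrawal (only about 100 enrolled overall). It is zero if nobody relapses, is rescued or leaves. With p = 80% and the relapse rates cited in the protocol's background taken as departures, the gap before rescue is 20 points at Month 3 (80 − 60) and 40 points at Month 6 (80 − 40), or less where relapse visits are windowed into the table. Rescue alone, at 0 to 30% of inactive subjects, adds 0 to 24 points when nobody has left (80 − 56). A reader might take these as a forecast of bias. They are illustrations on assumed inputs.

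Importance is minor: the endpoint is secondary and descriptive, and the primary endpoint is malignancy. It is a cheap improvement.

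**What to change.** Keep the planned tables. If withheld text already covers this, point to it. Otherwise add to SAP 5.9 one supplementary WAS table of clinically inactive disease off etanercept:

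- **Denominator at each visit:** all WAS entrants whose follow-up could have reached it, that is, 96 minus the extension month of withdrawal entry is at least the visit month (entry at Month 60 counts through withdrawal Month 36, since 96 − 60 = 36). Repeat it for the subset inactive at withdrawal entry.
- **Counted as not inactive from then on:** relapse leading to a re-treatment assessment visit, entry to re-treatment, or use of commercial etanercept or another biologic.
- **Other departures:** kept in the denominator and shown separately as status unknown.
- **Rescue:** split the inactive subjects at each visit into those with and without a DMARD newly started or added, or a new or increased systemic or intra-articular steroid, with a recorded JIA indication since withdrawal entry. Impose no permanent failure rule after a single injection.

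Use this table for any statement about disease control without etanercept.

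**Cost.** SAP wording, one more derived date and one table. Protocol 5.3 already records dates, dose, route and indication for DMARDs and corticosteroids. Two things need confirming:

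- The re-treatment assessment visit also serves subjects who leave for other reasons, so the end-of-phase form must identify relapse.
- Commercial etanercept must be captured during withdrawal. The withdrawal schedule says "For subjects in the withdrawal period, the following concomitant medications will be collected: DMARDs, corticosteroids, NSAIDs, and anti-infective agents" without naming anti-TNFs, as the observational note does. SAP 5.11 needs those dates anyway.

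The downsides are a less favourable rate and small numbers, so subtype tables should follow only if counts allow.
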